Patients who are eligible and consented to the study will be randomly assigned, after completing the baseline measurement, to either Usual Care or the Intervention, in a 1:1 allocation ratio. Randomization will occur in blocks of 8, using random numbers. Randomization will be stratified by whether the study participant is newly placed on the waiting list (defined as placement on the waiting list <6 months prior to enrollment) or has already been on the waiting list (defined as placement on the waiting list ≥6 months prior to enrollment). Random number sequences will be generated by the off-site study biostatistician ([name]). To promote allocation concealment, the biostatistician will allocate study participants to their study arm at the time of randomization and inform the study coordinator of the assigned study arm. The study coordinator will contact potentially eligible transplant candidates by telephone to inform them of their assignment. Study participants and the study coordinator will be aware of allocation to Usual Care or the Intervention group, but outcomes assessors will be blinded to the allocation group.

Study aims & objectives

The primary aim will compare LDKT readiness and LDKT receipt in the Intervention vs. Usual Care groups of our randomized clinical trial. Our primary outcome is change in readiness to pursue LDKT, and our main secondary outcome is actual receipt of LDKT after 18 months of follow-up. Other secondary aims will determine (a) the social and behavioral variables that modify the effect of the Intervention upon LDKT readiness and receipt; and (b) whether the intervention affects other precursors of LDKT readiness and receipt, such as knowledge about LDKT, self-efficacy, and other social and behavioral factors.

Data collection, follow-up and outcomes

Baseline Measurements

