Destination Transplant was developed by a transplant nephrologist, a social psychologist, a health communication researcher, and a graphic designer. Based upon the Transtheoretical Model (TTM) of Change⁴⁷, Destination Transplant is designed to increase both readiness to pursue LDKT and actual receipt of LDKTs among Black transplant candidates.

Destination Transplant Education Seminar

The intervention will include a single, 60-90 minute educational and motivational seminar, delivered to small groups of Black kidney transplant candidates and their family and friends (see Table 1 for details). The Intervention seminar will feature a slide presentation that includes brief talks from a physician, patient educator and patient ambassadors (donors and recipients). We anticipate that each seminar will include 3-5 listed transplant candidates, as well as family and friends. These seminars will be held at one of our two sites—Saint Barnabas Medical Center (SBMC), our main site, or our satellite location at Newark Beth Israel Medical Center. At the end of each Intervention seminar, we will measure the patients' perceptions of the cultural competence of the researcher and speakers. Additionally, at various different time points throughout the study period, patients will be given educational materials that were developed specifically for the Destination Transplant program. These education materials were modified based on early versions of stage-based, transplant education materials developed by the co-investigator ([name]) for her Explore Transplant and Your Path to Transplant educational programs.

We developed a slide presentation as the main method of education delivery. This interactive presentation provides patients with the opportunity to learn general information about CKD, the waiting list, and different types of kidney transplant. Facts about kidney disease, the waiting list, and transplant will be presented in a question and answer format in the slide presentation. Patients will be asked to respond to true/false and multiple-choice questions and receive nearly immediate feedback from the research team and the physician. The presentation focuses upon five types of kidney transplants that the transplant candidates can consider:

- 1) DDKT from a “standard” donor
- 2) “Nonstandard” DDKT (from donors with either a high kidney donor profile index (KDPI) or considered Public Health Service (PHS) increased risk)

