- 3) Multiple Listing at two or more transplant centers (DDKT at another transplant center in a different donation service area)
- 4) Direct LDKT
- 5) LDKT via Kidney Paired Donation (KPD)

The slide presentation education is designed to progress through the treatment options from least to more difficult, in terms of additional effort needed on the part of the patient. For instance, the first treatment option, DDKT from a standard donor, requires no additional action, given that each patient is already active on the DDKT waitlist. Each of the five transplant options will be discussed in detail, with concluding statements outlining the necessary steps for selecting each option.

Topics will include:

- *Basic facts about CKD, transplant, and the waiting list.* This portion of the presentation is designed to increase participant knowledge of CKD, LDKT, and living donation. Specific topics of this lecture include: •basic facts about CKD, •the kidneys, and dialysis; •benefits of transplant; •the DDKT waiting list and how it

- works; ●types of DDKTs, including high KDPI kidneys; ●and how to stay healthy and ready for a transplant.
- *The experience of receiving a transplant (by a Black recipient of a LDKT).* A recipient of a LDKT who is Black will speak about their own experiences. The exact content of the talk will vary according to the patient, but each talk will discuss the following: ●personal background; ●how the patient developed CKD; ●experience while on dialysis or with CKD; ●how they recruited a living donor; ●the transplant surgery and early post-transplant experience; ●current life with a transplant (advantages and disadvantages); ●how their living kidney donor is faring after donation; ●misconceptions about kidney transplant; and ●audience questions.
 - *The experience of serving as a living kidney donor (by a Black living kidney donor).* A living kidney donor who is Black will speak about their own experiences. The exact content will vary according to the donor, but each talk will discuss the following: ●personal background; ●how the donor became aware of the need for transplant by a loved one; ●why the speaker decided to become a live donor; ●testing and evaluations to become a donor; ●the actual donation operation; ●life after donation; and ●audience questions.

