 - *Ways to more quickly receive a transplant.* In addition to encouraging LDKT, we will encourage study participants in the Intervention arm to consider the following ways to more quickly receive a DDKT: ●accept a high KDPI kidney, if deemed medically appropriate; ●accept a PHS increased risk kidney; ●get on the DDKT waiting list at other transplant centers outside New Jersey and the SBMC donation service area.

Destination Transplant Education Folder

As a supplement to the slide presentation, patients will be given a folder to take home that contains factsheets that provide an overview of the five types of kidney transplant. Although

the content varies between the factsheets, all factsheets provide patients with instructions or further directions on what to do if they are interested in pursuing a particular option.

Destination Transplant Postcards

During the 9-month intervention period, patients will be sent one educational postcard per month that serves to provide both basic information about kidney disease and additional information about the five treatment options. These colorful postcards feature real recipients and donors and tackle tough topics including asking someone to get tested as a donor. The 9 postcards address the following topics:

- *“Your Exploration of Kidney Transplant Continues at Home”*. Welcomes patients and provides a short list of recommendations for patients who are waiting for a transplant
- *“Consider All Types of Kidneys for Transplant”*. Encourages patients to consider nonstandard deceased donor transplant through use of High KDPI donor kidneys
- *“Consider All Types of Kidneys for Transplant”*. Encourages patients to consider nonstandard deceased donor transplant through use of Public Health Service Increased Risk donor kidneys
- *“Learn About Living Donation”*. Encourages patients to reach out to others for support and to consider living donor transplant as a treatment option
- *“Learn Why People Want to Be Living Donors”*. Presents reasons why living donors may offer to help out a friend or a loved one.
- *“Compare the Risks and Benefits of Living Donation”*. Provides information about the risks (including costs, future impact on health, and risk of death) associated with donating a kidney
- *“Consider Getting a Transplant from a Living Donor”*. Provides a list of strategies that may be used to help an individual identify a potential donor

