Our initial analysis will be descriptive. Our main analysis will use standard intention-to-treat principles. First, we will describe participants’ baseline characteristics and compare

summary statistics of the Usual Care and Intervention groups. These summary statistics will include mean, standard deviation, median, and range for continuous variables, and counts and frequencies for categorical variables. Two-sample t-tests, Wilcoxon rank-sum tests (for non-parametric variables) and chi-squared tests will be used to test for differences between the Usual Care and Intervention groups, as appropriate.

For our primary outcome (increase in readiness to pursue LDKT), we will compare, using chi-square testing, the proportion of participants in the Usual Care vs. Intervention arms who have advanced at least one stage in their readiness to pursue LDKT (between the time of placement on waiting list and the time of reassessment at 18 months). For our main secondary outcome (receipt of LDKT), we will compare, using chi-square testing, the proportion of study participants in the Usual Care vs. Intervention arms who have received a LDKT. Sensitivity analyses will assess the intervention effect, adjusting for clustering of response by seminar group (because failing to account for clustering can reduce power)^{56,57}.

To determine which baseline factors (e.g. age), if any, modify the effect of the Intervention on the primary and secondary outcomes, logistic regression will model the log-odds of the outcome as a function of the intervention, while controlling for these factors of interest. Tests for modification by these key factors will be based on Wald tests of interaction terms between the intervention indicator and baseline factors. We will perform logistic regression⁵⁸ and model-building as we have in prior published analyses⁵⁹⁻⁶¹.

To test the effect of the intervention upon other precursors of LDKT readiness and receipt (e.g. knowledge about LDKT, self-efficacy, and other social and behavioral factors), we will use stratified chi-square tests for categorical variables and linear regression models for semi-continuous scales. The chi-square tests and linear regression models will be stratified by accumulated time on the waitlist at randomization (≤ 6 months vs. > 6 months). We will examine effects adjusted and unadjusted for baseline value for each respective scale.

Power and sample size calculations

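### The main tests ignore seminar clustering in the Intervention arm, and the reason given for adjusting only in sensitivity analyses is wrong for one-arm clustering (modest effect, ICC unstated)

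*Combined protocol and SAP*

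**What the plan says.** The section Statistical analyses specifies a plain chi-square for both key outcomes. For readiness: "For our primary outcome (increase in readiness to pursue LDKT), we will compare, using chi-square testing, the proportion of participants" in the two arms. For transplant receipt: "For our main secondary outcome (receipt of LDKT), we will compare, using chi-square testing, the proportion of study participants" in the two arms. Clustering appears only afterwards: "Sensitivity analyses will assess the intervention effect, adjusting for clustering of response by seminar group (because failing to account for clustering can reduce power". No model, variance estimator or ICC is given for that adjustment. One of the two references cited there (57) has a title about clustering effects due to treatment.

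Allocation is individual: "Patients who are eligible and consented to the study will be randomly assigned, after completing the baseline measurement". Grouping arises later, and only in the Intervention arm. On seminar size the plan says: "We anticipate that each seminar will include 3-5 listed transplant candidates, as well as family and friends". Usual Care has no seminar. Power and sample size calculations acknowledges that clustering in the Intervention arm may cost a little power, but Table 3 shows no allowance for it.

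Some features could raise the correlation within seminars and others could lower it. Of the live talk by a transplant recipient, the plan says: "The exact content of the talk will vary according to the patient, but each talk will discuss the following". Against that, "We developed a slide presentation as the main method of education delivery", and much of the programme is delivered individually: "During the 9-month intervention period, patients will be sent one educational postcard per month", and there is a coaching call about three months after baseline.

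**The concern.** A chi-square test assumes that participants' outcomes are independent. If people who sat in the same seminar tend to respond alike, the Intervention proportion is more variable than the binomial formula allows. The main test then uses too small a standard error, and any confidence interval reported with it is too narrow.

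The stated reason hides this. Ignoring clusters can cost power when each cluster contains both arms, as centres do, because the shared variation cancels out of the treatment comparison. Seminars contain one arm only, so nothing cancels and ignoring them makes the test reject too often. That clustering itself reduces power is a different statement. The power section makes it correctly. The parenthesis in Statistical analyses presents a validity question as a power question, which makes a sensitivity-only adjustment look sufficient. The plan has no rule for the case where the two analyses disagree, so the chi-square result would stand.

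**Working it through.** **Inputs.** From the plan: 250 or 200 per arm, 1:1 allocation, seminars of 3-5, control rates 0.10-0.40 for readiness and 0.14 for LDKT receipt. Assumed, because not stated: two-sided 0.05; ICC 0.01, 0.05 and 0.10; full seminar attendance unless noted.

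**1. Reproduce Table 3.** With p the control proportion, q the Intervention proportion, b = (p+q)/2, and a continuity correction of 1/n:

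power = Φ{[q − p − 1/n − 1.96·√(2b(1−b)/n)] / √([p(1−p)+q(1−q)]/n)}

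For 0.40 versus 0.55 at n = 200: (0.145 − 1.96×0.04994)/0.04937 = 0.954, so power is 0.83, as stated. All 18 entries agree within 0.01 with no clustering term. Without the correction, 0.10 versus 0.20 at 250 per arm gives 0.88 against the stated 0.85, so Table 3 appears to assume a corrected test. Statistical analyses does not say whether the test is corrected.

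**2. Type I error of the plain test.** With seminars of size m in one arm:

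- Design effect in the Intervention arm: DE = 1 + (m−1)·ICC·attendance
- True SE divided by assumed SE, under the null: r = √((1+DE)/2)
- True level: 2·(1 − Φ(1.96/r))

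Example, m = 4 and ICC 0.05: DE = 1.15, r = √1.075 = 1.037, level = 0.059.

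| ICC | m = 3 | m = 4 | m = 5 |
|---|---|---|---|
| 0.01 | 0.051 | 0.052 | 0.052 |
| 0.05 | 0.056 | 0.059 | 0.062 |
| 0.10 | 0.062 | 0.068 | 0.074 |

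At 70% attendance (assumed) and m = 4 the levels are 0.051, 0.056 and 0.062. Simulation with beta-binomial seminars in the Intervention arm and independent Usual Care agrees with the formula. For the continuity-corrected test, the simulated level over sizes 3-5 and control rates 0.10-0.40 is 0.034-0.043 at ICC 0.01, 0.040-0.051 at 0.05 and 0.045 to about 0.06 at 0.10.

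**3. Coverage and disagreement when the programme works.** Simulation of LDKT receipt 0.14 versus 0.24, 250 per arm, m = 4, uncorrected tests. Small ranges span repeated simulations.

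| ICC | Plain 95% interval covers | Plain significant, clustered not | Clustered significant, plain not |
|---|---|---|---|
| 0.01 | about 94.7% | about 1% | 0.8% |
| 0.05 | about 93.9% | 2.2-2.4% | 0.3% |
| 0.10 | about 92.8% | 4.1-4.4% | 0.1% |

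The cluster-robust interval covers 94.6-95.0%. At ICC 0.10 the rejection rate is 0.80 when clustering is ignored and 0.76 when it is accounted for, which is the opposite of the plan's parenthesis.

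**4. Table 3 with clustering.** Multiply the Intervention-arm variance by DE in the formula of step 1, with m = 4. For 0.40 versus 0.55 at n = 200 and ICC 0.05: (0.145 − 1.96×0.05178)/0.05122 = 0.850, so power is 0.80.

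| Scenario | Table 3 | ICC 0.01 | ICC 0.05 | ICC 0.10 |
|---|---|---|---|---|
| 0.40 v 0.55, 200/arm | 0.83 | 0.82 | 0.80 | 0.775 |
| 0.10 v 0.20, 250/arm | 0.85 | 0.85 | 0.83 | 0.80 |
| LDKT 0.14 v 0.24, 250/arm | 0.78 | 0.78 | 0.75 | 0.72 |

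Table 3 has 15 of 18 entries above 0.80. With m = 4 the counts are 15, 15 and 13 at the three ICCs; with m = 5 and ICC 0.05 the count is 14. If 80% retention also thins groups of four (3×0.8 = 2.4 remaining co-members), the first row becomes 0.81 at ICC 0.05 and 0.79 at ICC 0.10.

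**The case against.** The strongest reply is that the matter is largely in hand and the harm is small. An adjusted analysis is already planned, a reference on treatment-related clustering is cited, and a slight loss of power is disclosed. The following parts of that case stand:

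- **Size.** At ICC 0.05 the two analyses disagree in only about 2.5% of trials (2.2% + 0.3%), and the plan's statement that most scenarios exceed 80% power survives.
- **Continuity correction.** If the chi-square is corrected, as Table 3 suggests, inflation is essentially absent up to ICC 0.05.
- **Individual randomization.** If seminars affect nobody's outcome, the level is not inflated. Inflation needs seminar effects that vary between groups yet average to zero.
- **Choice of method.** Cluster-robust errors are one of several acceptable methods for clustering in one arm.

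A further point is that randomization is stratified by waiting time, while the plain chi-square ignores strata and so errs on the conservative side if strata differ. With equal strata and assumed LDKT rates of 0.08 and 0.20, the uncorrected level at m = 4 is 0.048 at ICC 0.01 and 0.055 at ICC 0.05, against 0.051 and 0.059 without strata. That offset rests on rates the plan does not give, and it vanishes if strata do not differ.

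None of this makes the stated reason right or justifies the independence assumption. Under-coverage of the plain interval does not need a null effect; it arises whenever seminar effects vary, including when the programme works. Statistical analyses specifies tests and no intervals, so this matters only if an interval is reported.

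**Conclusion.** The concern holds. The main tests of both outcomes ignore a dependence the plan itself acknowledges, and the reason given for the sensitivity analysis is wrong for seminars attended by one arm only.

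The consequence is modest and conditional on the ICC. At 0.01 it is negligible. From 0.05 upwards, disagreements between the two planned analyses mostly favour the plain test, which is the one the plan would report as its result. Power falls by about 2-3 points at ICC 0.05 with seminars of four, in the rows not already near 1.

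These figures rest on an assumed ICC range, a two-sided 0.05 level and, mostly, full attendance. The documents do not settle where the ICC lies. The change is worth making because it costs little and gives correct standard errors if clustering exists; the trial's design is not in question.

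**What to change.** - Make the main analysis of both outcomes a difference in proportions with standard errors clustered by seminar in the Intervention arm. Each attended seminar is a cluster; each Usual Care participant and each Intervention participant who attended no seminar is a cluster of one. Everyone is analysed as randomized.
- Keep the plain chi-square as the sensitivity analysis, and state whether it is continuity-corrected.
- Replace the parenthetical reason with one saying that ignoring clustering understates standard errors and can inflate type I error.
- Show Table 3 over a stated ICC range, such as 0.01-0.10.

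The cost is a change of wording and a revised table. The planned sensitivity analysis already needs seminar membership, so no extra patients or data are required. In simulation, intervals widen by about 0.5-1% at ICC 0.01, 2-6% at 0.05 and 5-11% at 0.10. At ICC 0-0.01 almost nothing is lost: the simulated level is 0.049-0.053 for the plain test and 0.050-0.054 for the clustered one, and power for LDKT 0.14 versus 0.24 at 250 per arm is about 0.82 (uncorrected) with either.

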The proportion of Usual Care (control) patients who have increased readiness for LDKT could plausibly range from 0.10 to 0.40, while the proportion who receives a LDKT is expected to equal 0.14 (based on prior baseline data from our center). Assuming there are 250 or 200 (assuming 100% and 80% retention rates) participants in each group, powers for increases of 0.10, 0.15, and 0.20 are presented in Table 3. In most scenarios, we have >80% power to detect a clinically significant increase in LDKT readiness and receipt of LDKT. We may be slightly underpowered only for very small increases in these two outcomes. Clustering by seminar in the Intervention arm may slightly reduce our power^{56,57,62}, but we should have sufficient power to detect an effect of the Intervention upon our LDKT readiness and receipt.

Abbreviations

CKD: Chronic kidney disease;

DDKT: Deceased donor kidney transplant;

ESRD: End-stage renal disease;

KDPI: Kidney donor profile index;

KPD: Kidney paired donation;

LDKT: Living donor kidney transplant;

OPTN: Organ Procurement and Transplantation Network;

PHS: Public Health Service;

SBMC: Saint Barnabas Medical Center;

TTM: Transtheoretical Model of Behavioral Change;

References

4. U.S. Renal Data System. *2017 USRDS Annual Data Report: Epidemiology of kidney disease in the United States*. Bethesda, MD: National Institutes of Health, National Institute of Diabetes and Digestive and Kidney Diseases;2017.

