Table 3. Power calculations for Primary and Main Secondary outcomes

Proportion among Controls	Proportion among Intervention	Power	
		250 participants per arm	200 participants per arm
Increase in readiness of at least one stage			
0.10	0.20	0.85	0.76
0.10	0.30	>.99	>.99
0.25	0.40	0.94	0.88
0.25	0.45	>.99	0.99
0.40	0.55	0.91	0.83
0.40	0.60	0.99	0.98
Receipt of LDKT			
0.14	0.24	0.78	0.68
0.14	0.29	0.98	0.95
0.14	0.34	>.99	>.99

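### Table 3 omits the 10-point readiness increase at control rates 0.25 and 0.40, where power is 0.48 to 0.65, so the claim of slight underpowering does not hold for the primary outcome

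*Combined protocol and SAP*

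**What the plan says.** The section Power and sample size calculations says that the proportion of Usual Care patients with increased readiness "could plausibly range from 0.10 to 0.40". It sets the sample size thus: "Assuming there are 250 or 200 (assuming 100% and 80% retention rates) participants in each group". It then states that "powers for increases of 0.10, 0.15, and 0.20 are presented in Table 3", and draws two conclusions. The first is "In most scenarios, we have >80% power to detect a clinically significant increase in LDKT readiness and receipt of LDKT". The second is "We may be slightly underpowered only for very small increases in these two outcomes".

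The section Statistical analyses names the test for the primary outcome: "we will compare, using chi-square testing, the proportion of participants in the Usual Care vs. Intervention arms who have advanced at least one stage". It gives no alpha or sidedness and does not say whether a continuity correction applies.

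In Table 3 the block headed "Increase in readiness of at least one stage" has six rows: 0.10 vs 0.20 and 0.30, 0.25 vs 0.40 and 0.45, and 0.40 vs 0.55 and 0.60. The block for LDKT receipt has all three increases at its single control rate of 0.14.

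**The concern.** Three control rates and three increases would make nine readiness rows, and six are printed. Of the three absent, two are the smallest listed increase at the middle and upper control rates. The third, 0.10 vs 0.25, is favourable to the trial, so there is no ground for suggesting selective omission.

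For a fixed absolute increase, power falls as the control rate moves toward 0.5. The one 0.10 row printed for readiness therefore sits at the end of the plausible range where power is highest. Table 3 and its accompanying paragraph are the only statement of power for the primary outcome. A reader deciding whether 200 to 250 per arm is enough, or later interpreting a null readiness result, could take it that a 10-point effect had been nearly covered across the plausible range.

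**Working it through.** **Inputs.** Control rates of 0.10, 0.25 and 0.40, increases of 0.10, 0.15 and 0.20, and n = 250 or 200 per arm come from Table 3 and the power section. The chi-square test comes from Statistical analyses, and 1:1 allocation from Randomization. Two-sided alpha 0.05, a pooled null variance and a 1/n continuity correction are inferred, because the documents do not state them.

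**Formula.** With d = p2 − p1 and p̄ = (p1 + p2)/2:

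- SE0 = √(2p̄(1 − p̄)/n)
- SE1 = √((p1(1 − p1) + p2(1 − p2))/n)
- Power = Φ((d − 1/n − 1.96·SE0)/SE1)

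**Reproducing the plan's figures.** For 0.10 vs 0.20 with n = 250, SE0 = √(2·0.15·0.85/250) = 0.0319 and SE1 = √((0.09 + 0.16)/250) = 0.0316. Power = Φ((0.10 − 0.004 − 0.0626)/0.0316) = Φ(1.06) = 0.855; Table 3 prints 0.85. Further checks, at 250 and 200 per arm:

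| Row | Table 3 | Corrected | Uncorrected |
|---|---|---|---|
| 0.10 vs 0.20 | 0.85, 0.76 | 0.855, 0.760 | 0.882, 0.802 |
| 0.25 vs 0.40 | 0.94, 0.88 | 0.939, 0.875 | 0.950, 0.896 |
| 0.40 vs 0.55 | 0.91, 0.83 | 0.907, 0.830 | 0.921, 0.854 |
| 0.14 vs 0.24 | 0.78, 0.68 | 0.783, 0.679 | 0.815, 0.724 |

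The corrected formula matches all 18 printed cells within 0.01. The uncorrected one does not, and one-sided 0.05 gives 0.933 and 0.878 for the first row. The inferred settings are therefore well supported.

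**The absent rows.**

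- 0.25 vs 0.35, n = 250: Φ((0.10 − 0.004 − 0.0803)/0.0407) = Φ(0.38) = 0.650
- 0.25 vs 0.35, n = 200: Φ((0.10 − 0.005 − 0.0898)/0.0456) = Φ(0.11) = 0.545
- 0.40 vs 0.50, n = 250: Φ((0.10 − 0.004 − 0.0872)/0.0443) = Φ(0.20) = 0.579
- 0.40 vs 0.50, n = 200: Φ((0.10 − 0.005 − 0.0975)/0.0495) = Φ(−0.05) = 0.480
- 0.10 vs 0.25: 0.991 and 0.971

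Uncorrected, the two 0.10 rows give 0.685 and 0.588, then 0.614 and 0.520. Exact binomial enumeration agrees. For 0.25 vs 0.35 it gives 0.651 and 0.546 with the Yates correction, and 0.685 and 0.590 with the plain Pearson test. For 0.40 vs 0.50 it gives 0.590 and 0.481, and 0.625 and 0.521.

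**Increase needed for 80% power**, at control rates 0.10, 0.25 and 0.40, by root-finding:

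| | 250 per arm | 200 per arm |
|---|---|---|
| Corrected | 0.092, 0.120, 0.129 | 0.106, 0.135, 0.144 |
| Uncorrected | 0.088, 0.115, 0.125 | 0.100, 0.130, 0.139 |

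**Where a 0.10 increase drops below 80% power.** Corrected, this happens above a control rate of 0.13 with 250 per arm and above 0.08 with 200, which covers the whole plausible range in the second case. Uncorrected, the thresholds are 0.15 and 0.10.

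**Cells above 0.80.** Of the 18 printed cells, 15 exceed 0.80; the exceptions are 0.76, 0.78 and 0.68. Adding three rows gives six more cells, two of them above 0.80, so the count becomes 17 of 24.

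**The case against.** The sentence at issue is hedged, and the plan does not say what counts as a very small increase. Since 0.10 is the smallest increase tabulated and no target effect is declared, the sponsor may have meant exactly that. The text says that three increases appear in Table 3, and they do; it does not promise every increase at every control rate. Some of the weakness is also visible: three of the four printed cells at a 0.10 increase are below 0.80. Because the formula is the same for both outcomes, the row 0.14 vs 0.24 shows what readiness power would be at a control rate of 0.14. Finally, the lowest figure, 0.48, needs a control rate of 0.40, 80% retention and the continuity correction together.

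Much of this stands. It rules out any claim that a printed number is wrong, that the trial misses a declared target, or that the general statement about most scenarios is false. It does not rescue the quoted sentence. Even if 0.10 counts as very small, the shortfall is not slight under either version of the test. The worst printed readiness figure is 0.76 and the worst anywhere in the table is 0.68; neither shows the depth of the shortfall at control rates 0.25 and 0.40.

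**Conclusion.** The concern holds. For a 0.10 increase in readiness at control rates 0.25 and 0.40, power is 0.48 to 0.65 with the continuity correction and 0.52 to 0.69 without it. The corrected figures are 15 to 32 percentage points short of 80%, the uncorrected ones 11 to 28. The fault lies in an incomplete table and an over-favourable summary sentence.

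The result rests on two-sided alpha 0.05 and on the continuity correction, both inferred from the match to Table 3; the conclusion does not depend on the correction. All figures are before clustering by seminar. The plan says clustering may reduce power but gives no intracluster correlation, so that loss is not quantified here.

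**What to change.** First, the sponsor should confirm the alpha, sidedness and continuity correction behind Table 3 and state them in the power section. If they are as inferred, add three readiness rows:

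| Control | Intervention | 250 per arm | 200 per arm |
|---|---|---|---|
| 0.10 | 0.25 | 0.99 | 0.97 |
| 0.25 | 0.35 | 0.65 | 0.55 |
| 0.40 | 0.50 | 0.58 | 0.48 |

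Keep the statement that most scenarios exceed 80% power. Replace the sentence about slight underpowering with wording such as:

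> With two-sided alpha 0.05 and a continuity correction, and before allowing for clustering, 80% power for readiness requires an absolute increase of about 9 to 13 percentage points with 250 per arm and about 11 to 14 with 200 per arm, depending on the control rate. Power for a 10-point increase in readiness ranges from 0.85 (control rate 0.10, 250 per arm) down to 0.48 (control rate 0.40, 200 per arm). For LDKT receipt, 0.14 vs 0.24, it is 0.78 and 0.68.

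If the sponsor confirms different settings, recompute these figures before printing them. The cost is three table rows, one replaced passage and a less favourable statement of power. No extra patients are needed.
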